7.3. Unscheduled Visits

If, during the investigation, a subject requires an unscheduled visit to the clinical site, the following information will be collected at a minimum:

- Chief complaint prompting the visit. If the reason is an adverse event, the applicable eCRF for the adverse event must be completed and subject record completed as appropriate
- Date and time of the visit and all procedures completed at the unscheduled visit
- Review of adverse event and concomitant medications

- Documentation of any test article dispensed or collected from the subject, if applicable
- Slit lamp findings (using the Slit Lamp Classification Scale)

If the Investigator withdraws a subject from the study, the final study visit case report forms must be completed indicating the reason(s) why the subject was withdrawn. The subject record must be completed documenting the date and primary reason for withdrawal and the study CRA notified.

Any ocular and non-ocular Adverse Events that are ongoing at the time of the study visit will be followed by the Investigator, within licensure, until they have resolved, returned to pretreatment status, stabilized, or been satisfactorily explained. If further treatment i.e., beyond licensure is required, the subject will be referred to the appropriate health care provider.

The following information will be collected during an unscheduled visit.

| Step | Procedure | Details | |
|------|----------------------------------------------------------------|------------------------------------------------------------------------------------------------------------------------------------------------------------------------------------------------------------------------------------------------------------------------------|--|
| U.1 | Chief Complaints | Record the subject's chief complaints for reasons for the unscheduled visit | |
| U.2 | Change of Medical History and Concomitant Medications | Questions regarding the change of subjects' medical history and concomitant medications. | |
| U.3 | Entrance VA | Record the entrance distance visual acuity (OD, OS and OU) to the nearest letter. | |
| U.4 | Subjective Sphero- cylindrical Refraction | The investigator will complete a subjective refraction (sphere and cylinder) and record the resultant distance visual acuity OD, OS, and OU to the nearest letter. | |
| U.5 | Slit Lamp Biomicroscopy | FDA Slit Lamp Classification Scale will be used to grade the findings. If no slit lamp finding is noted on the EDC form it is considered as a zero "0" Grade for all observations listed. After the slit lamp examination, at the discretion of the Investigator, rinse the | |
| | | subject's eyes thoroughly with preservative- free saline. | |
| U.6 | Dispensing (if applicable) | Additional lenses may be dispensed if one is lost or torn during the wearing period. | |
| U.7 | Exit Visual Acuity | Record the subject's exit distance visual acuity (OD, OS and OU) to the nearest letter. | |

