2. STUDY OBJECTIVES, ENDPOINTS AND HYPOTHESES

2.1. Objectives

Primary Objective(s)

The primary objective of this study is to compare the clinical performance of two study contact lenses using different curing techniques with respect to CLUE comfort and vision.

Other Objectives(s)

Other objectives of this study are to compare the clinical performance of two study contact lenses using different curing techniques with respect to driving, indoor and outdoor performance items, CLUE handling and the rate of Grade 3 or higher slit lamp findings.

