2.2. Endpoints

Primary Endpoint(s)

CLUE Comfort and Vision

The primary endpoints are overall quality of vision and overall comfort scores using Contact Lens User Experience (CLUE)TM questionnaire at the two-week follow-up. CLUE is a validated patient-reported outcomes questionnaire to assess patient-experience attributes of soft, disposable contact lenses (comfort, vision, handling, and packaging) in a contact-lens wearing population in the US, ages 18-65. Scores follow a normal distribution with a population average score of 60 (SD 20), where higher scores indicate a more favorable/positive response.

Other Observation(s)

Other endpoints are being evaluated chiefly to design future studies.

1. Driving Performance

Driving performance will be assessed by two individual patient reported outcome (PRO) questions at the 2-week follow-up evaluation. The individual items are as follows:

- A. Reduction in glare while driving during the day (Item ID: MIS00617)
- B. Reduction in glare while driving during the night (Item ID: MIS00618)

2. Indoor Performance

Indoor performance will be assessed by three individual patient reported outcome (PRO) questions at the 2-week follow-up evaluation. The individual items are as follows:

- A. Reduction in glare from the computer screen (Item ID: MIS00628)
- B. Reduction in glare caused by bright indoor lights (Item ID: MIS00625)
- C. Reduction in glare caused by bright light coming through the window (Item ID: MIS00626)

3. Outdoor Performance

Outdoor performance will be assessed by four individual patient reported outcome (PRO) questions at the 2-week follow-up evaluation. The individual items are as follows:

- A. Ability to see comfortably in bright sunlight (Item ID: MIS00613)
- B. Reduction in glare in bright sunlight (Item ID: MIS00614)
- C. Reduction in squinting in bright sunlight (Item ID: MIS00615)
- D. Reduction in eye strain in bright sunlight (Item ID: MIS00616)

All driving, indoor and outdoor (PRO) items above will be assessed using the same excellence scale of; 0: Not Applicable, 1: Excellent, 2: Very Good, 3: Good, 4: Fair and 5: Poor.

4. CLUE Handling

Handling scores will be assessed by using Contact Lens User Experience (CLUE)TM questionnaire at the two-week follow-up.

5. Physiological Response assessed at each visit.

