| CLUE Handling | CLUE handling of the step-cure and static cure lenses will be no different from each other. | | | |
| Physiological Response | Physiological responses of the step-cure and static cure lenses will be no different from each other. | | | |

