8.2. Withdrawal/Discontinuation from the Study

A subject will be withdrawn from the study for any of the following reasons:

- Subject death during the study period
- Subject withdrawal of consent
- Subject not compliant to protocol (e.g. Subject more than 2 days out of visit window).
- Subject lost to follow-up
- Subject no longer meets eligibility criteria (e.g. the subject becomes pregnant)
- Subject develops significant or serious adverse events causing discontinuation of study lens wear (subjects missing more than 2 days of missed lens wear within a period 1 of week should be discontinued)
- Subjects who have experienced a Corneal Infiltrative Event (CIE)
- Investigator's clinical judgment regarding the subject safety reasons (that it is in the best interest of the subject to stop treatment)
- Subject missed any scheduled study visits
- Subject not compliant with study lens wear schedule
- Subject not successfully dispensed due to lack of efficacy and safety including poor vision, poor comfort or unacceptable fit

For discontinued subjects, the Investigator will:

- Complete the current visit (scheduled or unscheduled)
- Complete the Final Evaluation, indicating the reason that the subject was discontinued from the study
- Record the spherocylindrical refraction with best corrected distance visual acuity
- Collect used test article(s) (worn or brought to the visit) from the subject and discard them, unless otherwise stated in Section 7.2
- Collect all unused test article(s) from the subject

An additional subject will be enrolled if a subject discontinues from the study prematurely.

In cases where a subject is lost to follow-up, every possible effort must be made to contact the subject and determine the reason for discontinuation/withdrawal. The measures taken to

follow up must be documented including two written attempts and a certified letter (or equivalent) as the final attempt.

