14. STATISTICAL METHODS

14.1. General Considerations

Statistical Analysis will be undertaken by the sponsor or under the authority of the sponsor. A general description of the statistical methods to be implemented in this clinical trial is outlined below.

All data summaries and statistical analyses will be performed using the SAS software Version 9.4, add/modify software if necessary (SAS Institute, Cary, NC). Throughout the analysis of data, the results for each subject/eye will be used when available for summarization and statistical analysis. Unscheduled visits will summarized separately and will be excluded from the statistical analysis.

Summary tables (descriptive statistics and/or frequency tables) will be provided for all baseline variables, efficacy variables and safety variables as appropriate. Continuous variables will be summarized with descriptive statistics (n, mean, standard deviation (SD), median, minimum and maximum). Frequency count and percentage of subjects or eyes within each category will be provided for categorical data.

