14.7. Other Exploratory Analyses

Driving, Indoor and Outdoor Performance

Each driving, indoor and outdoor performance item will be analyzed separately using a generalized linear mixed model for ordinal data with a multinomial distribution and cumulative logit as a link function. The experimental design factors: sequence of lens wear, period, lens type, first order carryover effect will be included in each model as fixed effects. Site will be included as a random effect. An appropriate covariance structure will be used to model the residual errors between measurements within same subject across study periods.

The assumption of proportionality of odds across response categories will be assessed graphically. If this assumption is violated then the distribution of responses will be investigated. If sparse data is observed then the sparse response categories may be collapsed to ensure there is sufficient data for analysis. If the assumption of proportionality of odds is still violated in the collapsed categories then a partial proportional odds model may be considered. If any of the above models fail to converge, then reduced versions may be considered. A Generalized Estimating Equation (GEE) may also be considered as necessary.

Comparison between the test lens and the control lens at the 2-week follow-up will be carried out using two-sided 95% confidence intervals of the odds ratios (Test over Control); where the odds ratio represents the odds of having a higher positive rating/experience for the Test lens compared to the Control lens.

For driving items, non-inferiority of the test lens relative to the control will be concluded if the lower limit of the 95% confidence interval of the odds ratio is above 0.67. If non-inferiority is met, then superiority will be tested. Superiority of the test lens relative to the control lens will be concluded if the lower limit of the confidence interval of the odds ratio is above 1.

CLUE Handling

CLUE handling will be analyzed and tested in the same exact manner as CLUE comfort and vision as describe above in Section 14.5.

Physiological Responses will be descriptively summarized for each lens type.

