14.9. Procedure for Handling Missing Data and Drop-Outs

Missing or spurious values will not be imputed. The count of missing values will be included in the summary tables and listings.

Subject dropout is expected to be one of the main reasons of missing data in this clinical trial. Past clinical trials don't provide the evidence that subject dropout is systematic or not-at-random. To evaluate the impact of missing data, sensitivity analysis will be conducted using multiple imputation methods if the proportion of subject dropout is greater than the 15%. The SAS/STAT procedures PROC MI and PROC MIANALYZE will be utilized with a parametric regression method used to make at least 10 imputations.

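### The by-lens rate of Grade 3 or higher slit-lamp findings, as planned, leaves out a finding first seen at an unscheduled visit that ends in withdrawal

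*Combined protocol and SAP*

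**What the plan says.** The relevant rules are spread over several sections of the combined protocol and SAP.

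- **Objective.** Section 2.1 lists, among the other objectives, a comparison of the lenses on "the rate of Grade 3 or higher slit lamp findings".
- **Endpoint and hypothesis.** Section 2.2 has "Physiological Response assessed at each visit", without saying whether unscheduled visits count. Section 2.3 adds: "Physiological responses of the step-cure and static cure lenses will be no different from each other".
- **Analysis.** Section 14.7 gives one line: "Physiological Responses will be descriptively summarized for each lens type". Section 14.1 says: "Unscheduled visits will summarized separately and will be excluded from the statistical analysis".
- **Unscheduled visits.** Section 7.3 includes slit-lamp findings in the minimum data set. Step U.5 then sets a default for all listed observations: "If no slit lamp finding is noted on the EDC form it is considered as a zero" grade.
- **Missing data.** Section 14.9: "Missing or spurious values will not be imputed".
- **Withdrawal.** Section 8.2 has a discontinued subject finish the visit in progress, which may be an unscheduled one, and then the Final Evaluation. The Final Evaluation steps shown in Section 7.2 (F.1 and F.2) are the exit form and a refraction. Table 3 marks slit-lamp biomicroscopy at baseline, follow-up and unscheduled visits, but not at Exit.

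**The concern.** Unscheduled visits are driven by complaints: step U.1 records why the subject came. A rule that removes them from a summary of severe slit-lamp findings is therefore not neutral, since it removes visits at which a finding is a plausible reason for attending.

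If the subject stays in the study, the wear period still has a scheduled slit-lamp value, though the grade may have fallen by then. If the subject is withdrawn at the unscheduled visit, the period has no scheduled value at all, and both the event and the period leave the by-lens rate. Any replacement subject adds new periods while the withdrawn one adds nothing. At stake is whether the Grade 3+ comparison named in Section 2.1 counts the events it is meant to count.

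**Working it through.** The documents state no Grade 3+ rate and no power or precision for this endpoint, so there is no planned figure to reproduce. The check is a trace through the text, followed by a scale calculation.

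**Trace of one case: Grade 3 finding between visits, subject withdrawn**

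1. The finding is graded at the unscheduled visit (Section 7.3, step U.5).
2. Under Section 8.2 the subject completes that visit and the Final Evaluation.
3. The Final Evaluation steps shown and the Exit column of Table 3 contain no slit lamp, so no later graded examination exists for that period.
4. Under Section 14.1 the unscheduled visit is summarised separately and excluded from the analysis.
5. The by-lens summary in Section 14.7 then holds neither the event nor the period.

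**What the Grade 0 default does**

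The default in U.5 applies when nothing is noted, so a noted Grade 3 remains Grade 3. It is written for visits that Section 14.1 already excludes, so under the current plan it can distort only the separate unscheduled summary. It would reach the by-lens rate only if unscheduled visits were brought in, which is why the two changes belong together.

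**Size of one event**

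- Inputs: about 90 enrolled and about 80 expected to complete (synopsis; Section 4.1); sequences Test/Control/Control and Control/Test/Test, randomised in blocks of 2 (Section 5.1).
- With 45 subjects per sequence: Test periods = 45 × 1 + 45 × 2 = 135; Control periods = 45 × 2 + 45 × 1 = 135; total 90 × 3 = 270. This is a maximum, since withdrawals shorten it.
- One event: 1/135 = 0.74 percentage points.
- With 40 completers per sequence: 40 + 80 = 120 periods per lens, and 1/120 = 0.83 percentage points.

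**Illustration of the total loss (both inputs assumed)**

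Let r be the true per-subject rate of Grade 3+ findings and u the share seen only at unscheduled visits. For 80 subjects, the expected number visible in scheduled-visit data is 80 × r × (1 − u).

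| r | All cases (80 × r) | Visible, u = 25% | Visible, u = 50% | Visible, u = 75% |
|---|---|---|---|---|
| 1% | 0.8 | 0.6 | 0.4 | 0.2 |
| 3% | 2.4 | 1.8 | 1.2 | 0.6 |
| 5% | 4.0 | 3.0 | 2.0 | 1.0 |

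The proportional loss equals u whatever r is. At these counts, one or two missing subjects could change how the two lenses compare.

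**The case against.** The other side has a good deal to say.

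- **The data are not lost.** The examination is mandatory at unscheduled visits, and those visits are summarised. This stands. However, the plan does not say that the separate summary is by lens or that it feeds the rate in Section 2.1.
- **Adverse-event reporting is a second route.** Section 13.1 lists corneal findings of Grade 3 or higher as significant adverse events, reportable to the sponsor within 24 hours, and Section 14.1 promises summaries of safety variables as appropriate. This also stands, but it does not close the gap. Section 14 specifies no by-lens adverse-event rate. The grade-based entry in Section 13.1 covers corneal findings only, whereas the slit-lamp examples in exclusion criterion 11 include tarsal abnormalities and conjunctival injection. The instruction to follow Grade 3 or 4 as an adverse event appears at Visits 2 to 4 and not in U.5.
- **U.5 may simply record negative findings.** Section 7.3 also asks for all procedures completed at the visit, so an examination not done should be traceable. That weakens the conflict with Section 14.9. An examination done but never entered would still read as normal.
- **Nothing inferential is at risk.** The endpoint is exploratory and descriptive, with no test, margin or model. This stands in full.

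A reader might infer that the Grade 0 default and the exclusion together record symptomatic Grade 3 cases as normal in the main comparison. The documents do not support that: the default cannot overwrite a noted grade, and it acts only on visits already excluded. Nor do they show that severe cases mostly present between scheduled visits.

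**Conclusion.** The point holds as a defined gap in an exploratory safety summary. Under the stated rules, a Grade 3+ finding first seen at an unscheduled visit that leads to withdrawal is absent from the by-lens summary, together with its wear period. This assumes that the Section 14.7 summary follows Section 14.1, which is the natural reading of a rule that summarises unscheduled visits separately.

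One omitted event is worth about 0.74 percentage points on a base of 135 periods per lens. The number of such events cannot be estimated from the documents. The effect could fall on either lens, so no direction for the difference between lenses can be claimed. What can be said is that the rate for the affected lens is understated.

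It would go too far to conclude that the trial's safety record is compromised or that the non-inferiority result is affected. The finding remains in the separate summary and, if corneal, in the adverse-event data, and Section 2.3 rests study success on CLUE comfort and vision alone. The change is still worth making, because the omission is selective, follows from a written rule and is nearly free to remove.

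**What to change.** 1. **Sections 14.1 and 14.7.** Define the Grade 3+ rate as the worst grade at any scheduled or unscheduled visit within a wear period, attributed to the lens worn in that period, with every dispensed wear period in the denominator. The follow-up slit lamp at Visits 2 and 3 precedes the next fitting, so it belongs to the period just ended. Report the number of dispensed periods with no graded examination beside the rate. Unscheduled visits can stay excluded from the CLUE analyses.
2. **Section 7.3, step U.5.** Require an explicit grade, including 0, for each observation, or 'not done', and treat blanks as missing. This brings U.5 into line with Section 14.9 and keeps default zeros out of the rate once unscheduled visits count.

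The cost is two sentences in Section 14, an EDC edit check, minor programming and a few more entries per unscheduled visit. No extra examination is needed, since the slit lamp is already required at those visits.

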7.4. Laboratory Procedures

The optical bench will be used to measure the light transmission characteristics for all worn Test lenses. The findings are for internal information only and will not be part of the final report.

8. SUBJECTS COMPLETION/WITHDRAWAL

8.1. Completion Criteria

Subjects are considered to have completed the study if they:

- provided informed consent
- completed all scheduled visits

8.2. Withdrawal/Discontinuation from the Study

A subject will be withdrawn from the study for any of the following reasons:

- Subject death during the study period
- Subject withdrawal of consent
- Subject not compliant to protocol (e.g. Subject more than 2 days out of visit window).
- Subject lost to follow-up
- Subject no longer meets eligibility criteria (e.g. the subject becomes pregnant)
- Subject develops significant or serious adverse events causing discontinuation of study lens wear (subjects missing more than 2 days of missed lens wear within a period 1 of week should be discontinued)
- Subjects who have experienced a Corneal Infiltrative Event (CIE)
- Investigator's clinical judgment regarding the subject safety reasons (that it is in the best interest of the subject to stop treatment)
- Subject missed any scheduled study visits
- Subject not compliant with study lens wear schedule
- Subject not successfully dispensed due to lack of efficacy and safety including poor vision, poor comfort or unacceptable fit

For discontinued subjects, the Investigator will:

- Complete the current visit (scheduled or unscheduled)
- Complete the Final Evaluation, indicating the reason that the subject was discontinued from the study
- Record the spherocylindrical refraction with best corrected distance visual acuity
- Collect used test article(s) (worn or brought to the visit) from the subject and discard them, unless otherwise stated in Section 7.2
- Collect all unused test article(s) from the subject

An additional subject will be enrolled if a subject discontinues from the study prematurely.

In cases where a subject is lost to follow-up, every possible effort must be made to contact the subject and determine the reason for discontinuation/withdrawal. The measures taken to

follow up must be documented including two written attempts and a certified letter (or equivalent) as the final attempt.

9. PRE-STUDY AND CONCOMITANT INTERVENTION/MEDICATION

Concomitant medications will be documented during screening and updated during the study. Disallowed medications for this study include: see Section 3.3.

Concomitant therapies that are disallowed include: see Section 3.3.

10. DEVIATIONS FROM THE PROTOCOL

Investigator will notify study sponsor upon identification of a protocol deviation. Major protocol deviations must be reported to the sponsor within 24 hours after discovery of the protocol deviation. The Investigator will report deviations per IRB/IEC requirements. All deviations will be tracked and corrective actions implemented as appropriate.

If it becomes necessary for the Investigator to implement a deviation in order to eliminate an immediate hazard to the trial subject, the Investigator may implement the deviation immediately without notification to the sponsor. Within 24 hours after the implemented deviation, the Investigator must notify and provide the rationale to the Sponsor and, as required, the IEC/IRB.

